# 10.1 Solicitation of AEs

At all follow-up visits occurring after study medication has been administered, the SAFETEE questionnaire [Johnson et al., 2005] will be used to assess AEs. The presence or absence of specific AEs should not be solicited from subjects.

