#### 7.1.3 Safety:

#### #S17-00949

Safety will be assessed by collection of adverse events using the Systemic Assessment for Treatment of Emergent Events (SAFTEE) [103] measure at all visits after treatment is initiated. LFTs will be obtained at screening, as well as weeks 2, 6 and 7 to assess the liver function during and after treatment with study medication. Risk of suicidality will be assessed by a licensed MD, NP, Psychologist, or C-SSRS certified study team member using the Columbia-Suicide Severity Rating Scale (C-SSRS) [98] as part of each study visit, including screening and baseline. If the patient endorses significant suicidality/homicidality, a safety assessment will be conducted, referrals provided, and if indicated, a case report form will be written if indicated, a follow-up phone call within 48 business hours of providing referrals will be completed. If and when appropriate, the clinicians will then contact the overall study PI ([name]) for further consultation. The appropriate procedures for all study team members to follow in the case of a psychiatric or medical emergency are outlined in detail in the Medical and Psychiatric Emergencies SOP.

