### 7.3.2 Enrollment/Baseline (B1) (Day 0, 1-30 days after Screening Visit)

- Perform alcohol breathalyzer to obtain BAC
- Record vital signs, results of examination, other assessments, concurrent medications and menstrual calendar (if applicable)
- Record AUD-related and PTSD related measures
- Collect imagery scripts for the cue/traumatic stress response task
- Collect urine for urine drug analysis and urine pregnancy test (if applicable)
- Collect baseline plasma for baseline CBD, THC, and AEA levels (pre-CBD dosing levels)
- Collect blood for carbohydrate deficient transferrin (CDT) test
- Record results of evaluations of safety and psychomotor effects and AUD, PTSD related domains
- Record adverse events as reported by participant or observed by investigator
- Evaluate and record alcohol use
- Administer medical management session
- Provide participants with study medication to administer at visit
- Provide participants with sufficient study medication to administer daily until the next scheduled visit (1 week), and instructions for how to use the study medication and document their use

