# 9 Specification of Safety Variables

Safety and toxicity monitoring will be performed throughout the study for all subjects. Safety variables to be assessed include AEs, vital signs, and safety laboratory values, when collected.

The occurrence of an AE or SAE may come to the attention of study personnel during study visits and interviews of a study participant presenting for medical care, or upon review by a study monitor. At each study visit following screening, designated study team members will inquire about the occurrence of AE/SAEs since the last visit.

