# **10 General Guidelines**

All AEs, regardless of causality or severity, must be immediately recorded on the AE CRF when volunteered by the subject or solicited through a study assessment questionnaire. The CRC will record all AEs, regardless of causality or severity, with start dates occurring any time after informed consent is obtained until 7 (for AEs) or 30 (for SAEs) days after the last day of study participation on the AE case report forms (CRF). Information to be collected includes event description, time of onset, clinician's assessment of severity, relationship to study product (assessed only by those with the training and authority to make a diagnosis), and time of resolution/stabilization of the event.

Any medical condition that is present at the time that the participant is screened will be considered as baseline and not reported as an AE. However, if the study participant's condition deteriorates at any time during the study, it will be recorded as an AE.

Changes in the severity of an AE will be documented to allow an assessment of the duration of the event at each level of severity to be performed. AEs characterized as intermittent require documentation of onset and duration of each episode.

At the last scheduled visit, the CRC should instruct each subject to report any subsequent event(s).

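### The structured AE questionnaire (SAFTEE) has no pre-dose reading and Section 20 has no treatment-emergent rule, so pre-existing symptoms can enter the AE count in both arms and dilute the primary safety contrast

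*Combined protocol and SAP*

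**What the plan says.** **Timing of SAFTEE.** Section 10.1: "At all follow-up visits occurring after study medication has been administered, the SAFETEE questionnaire" is the tool for assessing AEs. Section 7.1.3 likewise specifies the "measure at all visits after treatment is initiated". The baseline visit (Section 7.3.2) includes the first dose: "Provide participants with study medication to administer at visit". Its AE entry is "Record adverse events as reported by participant or observed by investigator", and it also lists results of safety and psychomotor evaluations. No section schedules SAFTEE before dosing.

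**Rules on pre-existing conditions.** Section 10 says that a medical condition present at screening "will be considered as baseline and not reported as an AE", unless it deteriorates. The AE definition in Section 8 includes an increase in the severity or frequency of a pre-existing abnormality. Section 10 records time of onset and collects AEs with start dates from informed consent onwards. Section 9 adds a general inquiry: "At each study visit following screening, designated study team members will inquire about the occurrence of AE/SAEs since the last visit".

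**How specific the questioning may be.** The sentence after the SAFTEE instruction in Section 10.1 reads: "The presence or absence of specific AEs should not be solicited from subjects".

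**Analysis.** The Protocol Summary lists AEs among the primary endpoints. Sections 20.3.2 and 20.3.4 tabulate AE frequency by arm and compare it with chi-squared tests; Section 20.3.2 does so over all time points. Neither defines a treatment-emergent event. Section 20.3.8 describes the primary outcomes as safety data for which no difference between arms is hypothesised.

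**The concern.** In patients with alcohol use disorder and PTSD, complaints such as poor sleep, fatigue and stomach upset may well be present before treatment. If a structured instrument first asks about symptoms after the dose, some long-standing complaints can be heard for the first time on treatment and dated wrongly. The error would be similar in both arms, so it raises both event rates and shrinks the difference between them.

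In most comparisons dilution works against the hypothesis. Here it works in its favour, because the expected result is no difference. Several events that the risk section lists as seen with CBD (somnolence, fatigue, lethargy, diarrhea, decreased appetite) could plausibly overlap with background complaints, so a real excess on CBD would be harder to see in the tables as well as in the test. A pre-dose reading that was not taken cannot be recovered at analysis.

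**Working it through.** **1. Is there a usable pre-dose baseline for AEs?**

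| Source | What it provides | What it lacks |
|---|---|---|
| Medical history and examination (7.1) | Conditions known at screening | Not the SAFTEE instrument; not at first dose |
| AE inquiry at visits after screening (9) | Events since the last visit | Not a reading of current symptoms |
| B1 AE entry (7.3.2) | Reported or observed events | Not SAFTEE |
| BAI, BDI-II and PCL-5 at baseline (4.2.2) | Anxiety, mood and PTSD symptoms | No stated link to AE classification |
| Clinical re-screen (7.3.6) | Listed eligibility checks | No general symptom inventory |

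The reference point in Section 10 is screening. B1 follows 1-30 days later (7.3.2), and Section 7.3.6 provides for delays of more than 3 months. The exclusion rule exists, but there is no like-for-like pre-dose reading to apply it to.

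**2. Does the analysis close the gap?** AEs are collected from consent. Section 20 does not say whether an event with onset before the first dose is dropped, or how baseline severity is used.

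**3. Size of the dilution.** The plan states no AE rate, margin or AE power, so there is no figure of its own to reproduce. The power statement in Section 20.4 concerns a t test of means.

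Inputs from the documents: 30 CBD and 18 placebo; two-sided 0.05 (20.3.1); chi-squared test (20.3.2). Assumptions, none from the documents:
- The true rate p of a new or worsened symptom is 35% on CBD and 5% on placebo.
- Background prevalence b is 30-50% in both arms.
- A share L of background symptoms is wrongly counted as on-treatment.
- The unit is participants with the event.
- The test has no continuity correction.

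Observed rate: q = 1 - (1 - p)(1 - bL). The risk difference becomes (0.35 - 0.05)(1 - bL). For b = 0.30 and L = 1, CBD is 1 - 0.65 x 0.70 = 0.545, placebo is 1 - 0.95 x 0.70 = 0.335, and the difference is 0.30 x 0.70 = 0.21. Power is the sum of binomial probabilities over all 2x2 tables in which the statistic reaches 3.841.

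| L | b = 30%: CBD v placebo | Power | b = 50%: CBD v placebo | Power |
|---|---|---|---|---|
| 0 | 0.350 v 0.050 | 0.744 | 0.350 v 0.050 | 0.744 |
| 10% | 0.370 v 0.079 | 0.653 | 0.383 v 0.098 | 0.602 |
| 25% | 0.399 v 0.121 | 0.546 | 0.431 v 0.169 | 0.459 |
| 100% | 0.545 v 0.335 | 0.285 | 0.675 v 0.525 | 0.188 |

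**4. Sensitivity.**
- Other true rates: with 10% v 50%, power is 0.86 with no miscounting. It falls to 0.48 when 30% of participants are counted regardless of drug effect, and to 0.31 when 50% are. With 20% v 50%, the figures are 0.54, 0.31 and 0.21.
- What is counted: the 0.744 requires worsening to be as detectable as new onset. If only brand-new symptoms count, the rates are p(1 - b) and power is 0.520 at b = 30% and 0.293 at b = 50%.
- Continuity correction: with Yates and b = 50%, counting only new symptoms gives 0.092, against 0.106 with no baseline at all. The gain therefore depends on counting worsening as well.

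**The case against.** The protocol already has much of the logic. Sections 8 and 10 treat existing conditions as baseline unless they worsen and require onset dates. Staff ask about AEs before SAFTEE begins, and anxiety, mood and PTSD symptoms are measured at baseline. The safety analysis is described as largely descriptive, AEs are also tabulated by relatedness and severity, and Section 20.1 promises a formal SAP before lock. All of this stands, and it limits the problem. It does not supply the missing reading or the missing counting rule, and inflated background rates blur descriptive tables too.

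Four stronger readings are tempting, and the documents do not support them.
- A reader might infer that background symptoms will surface as on-treatment events. The text supports only that they can. The instruction that "The presence or absence of specific AEs should not be solicited from subjects" would reduce prompting if followed, although it sits awkwardly beside a structured questionnaire.
- A reader might infer that fluctuating symptoms automatically become new events, because "AEs characterized as intermittent require documentation of onset and duration of each episode". That sentence governs events already classed as AEs; it does not override the baseline rule.
- A reader might infer that the gap protects a broad prediction of no excess side effects in Section 3.1. That prediction is confined to psychomotor and other motor effects, and Hypothesis 1a is also narrower. The general null statement is the one in Section 20.3.8.
- A reader might take 19-29% as the expected power. It requires the Section 10 exclusion to fail every time.

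**Conclusion.** The point holds as a gap in measurement and in analysis definition. SAFTEE starts after dosing, the baseline exclusion therefore depends on history, general inquiry and recall, and Section 20 does not say which recorded AEs count. Miscounting of similar size in both arms would move the safety contrast towards the hypothesised null.

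The direction is clear but the size is not. With the assumed 35% v 5% and 30-50% background, miscounting 10-25% of background symptoms lowers power from 74% to 46-65%; the 19-29% figure is the worst case. These figures show how sensitive the comparison is; they do not forecast this trial's power. Given the descriptive weight of the safety analysis and the small sample, this is an inexpensive improvement that is worth making. It does not invalidate the safety endpoint.

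**What to change.** 1. In Sections 7.1.3, 7.3.2 and 10.1, schedule SAFTEE once at B1, before the first dose.
2. In Sections 20.3.2 and 20.3.4, and in the formal SAP, define as treatment-emergent only events that start after the first dose or are worse in severity or frequency than at B1. Use that set for the comparison between arms, and list events with onset between consent and first dose separately. Keep the worsening clause, because counting only new symptoms gives up much of the gain.
3. Reconcile the two sentences of Section 10.1, so that staff know how SAFTEE is to be given if specific events are not to be solicited. Use the same approach at B1 and afterwards.

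Cost: about 48 extra questionnaires, a few minutes per participant at a visit already held, and one SAP definition.

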# 10.2 Preplanned Hospitalization or Procedure

During the study, if a subject has a hospitalization or procedure (e.g., elective surgery) that was due to a preexisting condition that has not worsened since enrollment in the study (i.e., since the subject [or the subject's legal representation] signed the informed consent), the hospitalization or procedure is considered a therapeutic intervention and not the results of an AE. However, if the event/condition worsens during the study, it must be reported as an AE (or SAE, if the event/condition results in a serious outcome, such as hospitalization).

# 10.3 Reports of Cancer

Cancer is no longer considered an FDA criterion for an SAE (unless an event occurs with a serious outcome). If a new diagnosis of cancer has a serious outcome, then the reporting time frame for an SAE (48 hours) must be met. Progression of disease is not considered new cancer and is therefore not an AE.

# 10.4 Specific guidelines for assessing laboratory values as adverse events

Any laboratory abnormality, including leukopenia, absolute neutropenia, or thrombocytopenia, will not be considered an AE unless this abnormal laboratory value results in clinical sequelae, such as infection, bleeding, or an intervention. If an abnormal laboratory value results in a clinical event, then the clinical event, not the abnormal laboratory value, must be recorded as an AE. The clinical event must be reviewed to determine if it meets the criteria for an SAE.

# **11 Assessment of Adverse Events**

#S17-00949

The following definitions, developed in accordance with the US Code of Federal Regulations (CFR) and the International Committee on Harmonization (ICH), will be used for the purpose of identifying AEs in this clinical study.

# 11.1 Expectedness

Unexpected: An AE is considered unexpected if it is not listed in the Investigator Brochure (IB) or is not listed at the specificity or severity that has been observed, or not previously observed in animal toxicity studies for psilocybin. Unexpected also refers to AEs that are mentioned in the IB as occurring with a class of drugs or as anticipated from the pharmacologic properties of the drug, but are not specifically mentioned as occurring with psilocybin.

# 11.2 Severity

The determination of severity must be made with the appropriate involvement of a medically qualified investigator. The investigator will evaluate the severity of each AE using the following three terms and definitions:

- Minimal: single occurrence that is not distressing and does not limit activities
- Mild: multiple occurrences, awareness of sign or symptom but easily tolerated, usually does not require intervention or limit activities
- Moderate: discomfort sufficient to cause interference with normal activities; intervention may be needed
- Severe: incapacitating, with inability to perform normal activities; treatment or other intervention usually needed

# 11.3 Relatedness

This category provides the opportunity to indicate the reasons for suspecting a drug-related effect. If no such effect is suspected, check "No." The following reasons for possible relationship to drug are to be assessed by the medically qualified investigator.

- Dose-response: indicates that the intensity of the event is related to the dosage level.
- Timing of onset: is used if the onset of the event has some regular relationships to drug administration (e.g., it always occurs 1 hour after taking the drug).
- Known drug effect: is another reason for suspecting a drug relationship.

The relationship of each AE to study drug will be assessed using the following terms and definitions:

- Probable (must have first two): This category applies to AEs that are considered, with a high degree of certainty, to be related to the study drug. An AE may be considered probable, if:
  - It follows a reasonable temporal sequence from administration of the drug.
  - It cannot be reasonably explained by the known characteristics of the subject's clinical state, environmental or toxic factors, or other modes of therapy administered to the subject.
  - o It follows a known pattern of response to the suspected drug.
- Possible: This category applies to those AEs in which the connection with the study drug administration is possible. An AE may be considered possible if, or when, any of the above reasons have been selected.
- Unrelated: This category is applicable to those AEs that are judged to be due only to extraneous causes (e.g., disease, environment, etc.) and do not meet any of the criteria for a possible drug relationship.

The determination of the relationship of the AE to the use of the study drug(s) rests on careful medical consideration of the PI.

# **12 Monitoring Adverse Events**

The investigator will follow all AEs until the event is resolved, stabilized, or the subject is lost to follow-up. Relevant
clinical assessments and laboratory tests may be performed as determined by the PI or a qualified designee, appropriate medical intervention should be provided and, if necessary, the subject may be excluded from additional treatment with the study drug.

Any actions taken and follow-up results must be recorded on the appropriate page of the CRF and in the subject's source documentation. Follow-up laboratory results should be filed with the subject's source documentation.

For all AEs that require the subject to be discontinued from the study, relevant clinical assessments and laboratory tests will be repeated as clinically appropriate, until final resolution or stabilization of the event(s).

# **13 Known Potential Toxicities of Study Drug**

Overall, no preclinical results have been identified that preclude the development of cannabidiol for the treatment of alcohol use disorder, or suggest that serious AEs are likely in clinical studies. Refer to the IB for toxicology findings and information on AEs observed to date.

# 14 Other Significant Adverse Events

Should any AE occur that is considered significant, but does not meet the criteria for an SAE, the CRC and PI should be notified immediately.

# **15 Reporting Procedures**

## 15.1 AE Reporting

To the FDA: In accordance with FDA reporting requirements, all AEs occurring during the course of the clinical trial will be collected, documented, and reported by the PI or IND Sponsor. On an annual basis, as part of the update to the study IND, the IND Sponsor will submit to the FDA:

- A list of all AEs that have occurred during the reporting period
- A summary of all IND safety reports submitted during the past year
- A list of all subjects who died during the participation in the investigation, listing cause of death for each,
- And a list of subjects who dropped out during the course of the investigation in association with any adverse experience, whether or not thought to be drug related.

To the IRB: In accordance with local IRB requirements, all AEs occurring during the course of the clinical trial regardless of relationship to study activities will be collected, documented, and reported by the PI or designee to the IRB on an annual basis in the application for the study's continuation renewal. Staff education, re-training or appropriate corrective action plan will be implemented when unreported or unidentified AEs or SAEs are discovered, to ensure future identification and timely reporting.

To the DSMB: All AEs occurring during the course of the clinical trial regardless of relationship to study activities will be reported to the DSMB at regular meetings. Prior to each DSMB meeting, the PI will prepare a report to the Board including review of aggregate analysis of AEs and SAEs.

Following each meeting, the board will provide the PI with a report including a recommendation to continue the study unchanged, continue with modifications of the protocol and/or the consent form to protect participant safety, or terminate the study. This report will then be submitted to the FDA as part of the annual report to the study IND, and the IRB in the application for the study's annual continuation renewal.

### To the Study Sponsors:

Tilray

The PI shall promptly inform Tilray of any significant safety issues occurring during the course of the study that might affect the performance of the study and of any AEs and SAEs experienced by subjects during the study. The PI shall share with Tilray any associated CRFs and source data, safety reports related to such AEs and SAEs,

Version: 4.3 and permit access to anonymized pharmacokinetic data of study subjects.

PI shall provide all reports issued by the DSMB according to protocol (e.g. annually for the duration of the trial, including prior to enrollment of the first participant, following completion of treatment for the first 5 completers, after completion of treatment for the first 20 completers, and upon completion of enrollment for the trial).

#### NIH/NIAAA

All AEs occurring during the course of the clinical trial regardless of relationship to study activities will be collected, documented, and reported by the PI or designee to NIH/NIAAA on an annual basis in the annual Research Performance Progress Report (RPPR).

## 15.2 SAE Reporting

SAEs will be promptly reported to the CRC and PI. The PI or qualified designee will distinguish Serious Adverse Events (SAEs) from Adverse Events (AEs). The details of the event will be documented and reported as follows:

To the FDA: The PI is required to report certain study events in an expedited fashion to the FDA. These written notifications of AEs are referred to as IND/IDE safety reports.

The following describes the IND safety reporting requirements by timeline for reporting and associated type of event:

- Within 7 calendar days (via telephone or facsimile report)
  - Any study event that is:
  - associated with the use of the study drug
  - unexpected, and
  - fatal or life-threatening
- Within 15 calendar days (via written report) Any study event that is:
  - associated with the use of the study drug,
  - unexpected, and
  - serious, but not fatal or life-threatening
    -or-
  - a previous AE that was not initially deemed reportable but is later found to fit the criteria for reporting (reporting within 15 calendar days from when event was deemed reportable).

Any finding from tests in laboratory animals that:

 suggest a significant risk for human subjects including reports of mutagenicity, teratogenicity, or carcinogenicity. This is not applicable for us as we are not using animals in this study.

Each written notification must be submitted on an FDA Form 3500A. The PI is also required to identify in IND safety reports all previous reports concerning similar AEs and to analyze the significance of the current event in light of the previous reports.

To the IRB: The IRB Chair or Administrator will be notified immediately for SAEs that are at least possibly related to study participation only. If the IRB administrator determines that reporting of the incident/issue is required, it will be submitted to the IRB within 48 hours of the IRB direction/response.

The team will also submit summary information related to all SAEs, AEs, and UPs in the annual application for continuation to the IRB.

